## **General Information/ Background**

General anesthesia is a complex physiological state characterized by reversible loss of consciousness, whole-body analgesia, amnesia, and muscle relaxation. The term low-flow anesthesia describes inhalation anesthesia techniques that are administered with a semi-closed rebreathing system and have a rebreathing rate of at least 50%. The high standard of anesthesia machines, the existence of monitors that analyze the anesthetic gas composition continuously and in detail, and the increased knowledge about the pharmacodynamics and pharmacokinetics of inhalation anesthetics have greatly facilitated the safe administration of low-flow anesthesia. The terminology associated with low-flow anesthetic techniques may be based on rebreathing or fresh gas flow rates. The fresh gas flow rate is the most critical factor determining the rebreathing rate. Most patients can have low-flow anesthesia when modern re-breathing systems are used; the fresh gas flow rate is reduced to less than 2 L/min. Oxidative stress is accepted as a pathological mechanism. Oxidative stress is a state of oxidative damage that occurs when the critical balance between free radical production and antioxidant defense systems is disrupted. Oxidative stress is beneficial in certain physiological conditions. For example, it can strengthen biological defense mechanisms during appropriate physical exercise and ischemia. However, its benefits are limited to these specific situations, and in many other cases, high levels of oxidative stress cause cell death and, thus, cell and tissue damage through necrotic or apoptotic mechanisms. If damage continues at the cell and tissue level, it causes various organ damage and disease onset and progression. In our study, the amount of inspired oxygen is expected to be low due to keeping the gas supplied to the system low in low-flow anesthesia applications. Accordingly, the oxidative stress will be less. Therefore, this study will investigate whether low-flow anesthesia positively contributes to the total oxidant/antioxidant balance.

**Keywords:** General anesthesia, low flow anesthesia, oxidative stress

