### *Exclusion criteria:*

ASA III and above patients,

Patients for whom an Intensive Care Unit (ICU) indication is foreseen

Chronic obstructive pulmonary disease,

A personal or family history of malignant hyperthermia,

Morbid obesity,

Alcohol or drug addiction,

History of liver or kidney disease,

With coronary artery disease or heart failure,

Significant anemia or hemoglobinopathy,

Hypotension, hypovolemia, sepsis.

After the patients who meet the specified criteria are informed about the study, volunteers who agree to participate and sign an informed consent will be included. Vitamin D, albumin, CRP, Total Antioxidant Status (TAS), and Total Oxidant Status (TOS) levels will be measured in the blood samples obtained from all volunteers' preoperative routine blood samples. After all volunteers are admitted to the operation room, they will be monitored with electrocardiography, pulse oximetry, non-invasive blood pressure, end-tidal carbon dioxide, temperature probe, and processed electroencephalogram- -bispectral index (BIS) without any medication. Baseline peak heart rate (HR), peripheral oxygen saturation (SpO2), systolic (SBP) and diastolic blood pressure (DBP), end-tidal carbon dioxide (ETCO2), body temperature, and BIS will be recorded. All measurements will be repeated and recorded at 5-minute intervals during the operation.

Volunteers will be divided into low-flow group (D) and high-flow group (Y). D group will receive 1 L/min fresh gas flow, and Y group will receive 4 L/min fresh gas flow. Processed EEG values of all patients will be monitored during the operation and ensured they are at the same depth of anesthesia. Albumin, CRP, TAS, and TOS values will be rechecked in the postoperative blood samples of the patients during and after the operation and compared with the previous values.

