#### **Statistical Analysis Plan**

The Shapiro-Wilk test will be used to check the normal distribution of the numerical data, and the kurtosis and skewness coefficients will also be examined. Variance homogeneity will be analyzed using Levene's test. Independent samples t-test, Welch test, or Mann-Whitney U test will compare the groups depending on the data distribution. Depending on the expected value rule, categorical variables will be analyzed using Pearson chi-square, Fisher's exact, or Fisher-Freeman-Halton tests. A comparison of the values measured at different periods during the operation will be performed using repeated measures ANOVA. Pearson correlation or Spearman's rho will be used in correlation analyses depending on the data distribution. Descriptive statistics will be given as mean±standard deviation or median, quartiles, and minimum-maximum values depending on the data distribution, and categorical variables will

be summarized as numbers and percentages. Statistical analyses will be performed using SPSS v.22 (IBM Corp. Released 2013. IBM SPSS Statistics for Windows, Version 22.0. Armonk, NY: IBM Corp.) package program, and the significance level will be taken as 0.05.

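### Correlations are planned without a flow-group term and without saying whether the arms are combined; if they are, a flow effect on both markers of a pair can create or hide a correlation

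*Combined protocol and SAP*

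**What the plan says.** The Statistical Analysis Plan states: "Pearson correlation or Spearman's rho will be used in correlation analyses depending on the data distribution". The only choice it describes is between the two coefficients, and that choice rests on distribution. It does not name the marker pairs or the time points, it does not say whether the arms are analysed together or apart, and it plans no partial or stratified coefficient. Group enters that section only through the two-sample and categorical tests. For all analyses, "the significance level will be taken as 0.05".

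The design has two arms. Material and Methods (the text following the exclusion criteria) says "D group will receive 1 L/min fresh gas flow, and Y group will receive 4 L/min fresh gas flow". On timing, the same text says that vitamin D, albumin, CRP, TAS and TOS "levels will be measured in the blood samples obtained from all volunteers' preoperative routine blood samples", and later that "Albumin, CRP, TAS, and TOS values will be rechecked in the postoperative blood samples of the patients during and after the operation". Four markers are therefore measured again once the assigned flow has had a chance to act.

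General Information/Background gives the expectation for low flow: "Accordingly, the oxidative stress will be less". It gives the aim as "this study will investigate whether low-flow anesthesia positively contributes to the total oxidant/antioxidant balance". It states a direction but no effect size.

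**The concern.** The trial is built to find out whether flow moves oxidant and antioxidant markers. If it moves two of them, the patients form two clouds displaced from each other. A single Pearson or Spearman coefficient over both clouds picks up the displacement as well as the relation between the markers from patient to patient within an arm.

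The displacement alone can then make unrelated markers look related, or cancel a relation that exists. A reader would take such a coefficient as a statement about biology, for instance how TAS and TOS move together after surgery, when part of it reflects which arm the patients were in. Choosing between Pearson and Spearman by distribution gives no protection, because ranks carry the same displacement.

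**Working it through.** The plan gives no correlation, effect size or power for these analyses, so there is no figure of its own to reproduce. The check is of the mechanism, under stated assumptions.

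**Inputs from the document.** Two flow groups; plain Pearson or Spearman; significance level 0.05. Sidedness is not stated, and two-sided is assumed.

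**Assumptions.** Equal groups, 40 per group (80 in total), with totals of 60 and 100 as a range; normally distributed markers; flow effects d1 and d2 on the two markers, in within-arm SDs; within-arm correlation rho. The text available for review has no sample size. It is not complete, so that absence is not held against the plan.

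**Formula.** For two equal groups combined:

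r = (rho + d1·d2/4) / sqrt[(1 + d1²/4)(1 + d2²/4)]

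**1. Creating a correlation** (rho = 0, shifts +d and -d). The formula reduces to r = -(d²/4)/(1 + d²/4).

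| d | combined r | false positives, 40 per group |
|---|---|---|
| 0.5 | -0.0625/1.0625 = -0.059 | 8.2% |
| 0.8 | -0.16/1.16 = -0.138 | 23.5% |
| 1.0 | -0.25/1.25 = -0.200 | 43.8% |

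The rates come from 20,000 simulated trials per row; the coefficient adjusted for group stayed at about 5%. Shifts in the same direction give the same sizes with a positive sign.

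A separate simulation (10,000 runs) brackets these rates. With 60 patients in total the rates at 0.5, 0.8 and 1.0 SD were 7.5%, 18% and 33%; with 100 they were 9%, 28% and 53%. Spearman was nearly identical (18.1% against 18.2% at 0.8 SD with 60 patients). The partial correlation stayed between 4.6% and 5.4% over all settings tried (40 to 150 patients, d from 0 to 1.5).

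**2. Hiding a correlation** (rho = 0.30, opposite shifts of 0.8 SD). r = (0.30 - 0.16)/1.16 = 0.12. With 40 per group, power is about 18% for the combined coefficient and about 77% for the adjusted one. At 0.5 SD the combined r is (0.30 - 0.0625)/1.0625 = 0.22, a milder loss.

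**3. Only one marker shifted** (d2 = 0). The product term vanishes, so with rho = 0 the combined r is 0. With rho = 0.30 and d1 = 0.8, r = 0.30/sqrt(1.16) = 0.28. This covers preoperative vitamin D paired with a later marker.

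**4. Both values preoperative.** The assigned flow has not yet been given, so it produces no shift: d1 = d2 = 0 and r = rho.

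**The case against.** The strongest reply is that the plan nowhere says the arms will be combined. Coefficients computed within each arm fit the sentence equally well and have none of this problem. That stands: a reader might infer that the planned coefficient is biased, but the text supports only that the handling of the arms is left open. The gap still matters, because the choice would otherwise be made once the data are in hand.

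Other strong readings also go too far:

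- **That every statement about how the markers move together would be wrong.** Steps 3 and 4 above rule this out for preoperative values and for pairs with only one shifted marker.
- **That the trial's hypothesis implies a distorted coefficient.** The background expects less oxidative stress and asks about the balance; it does not say that TAS will rise. A fall in TOS alone could improve the balance and would create no spurious correlation with TAS.
- **That repeated samples from one patient will be entered as separate observations.** Nothing in the plan says so. Stating one value per patient is a clarification, not the correction of a stated error.

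A combined coefficient is also a legitimate description of the marginal association in the whole sample, so preferring the within-arm association is a choice of target. That is fair. But the plan does not say which it wants, and the within-arm association is the one readers are likely to take from a correlation between markers. Finally, no stated aim depends on a correlation, which limits the consequence.

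**Conclusion.** The point holds in a conditional form. The plan names plain coefficients with no flow-group term. They mislead about the within-arm association when three conditions are met together: the arms are combined, the values are taken during or after exposure (or are changes), and flow shifts both markers.

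Under those conditions, with 40 per group assumed, the distortion is minor at 0.5 SD and material from about 0.8 SD on both markers, where the false-positive rate reaches about 24% and a true correlation of 0.30 shrinks to about 0.12. These sizes rest on assumed effects, equal groups and an assumed sample size. The mechanism itself needs only the three conditions. The between-group comparison of TAS, TOS, CRP and albumin is not affected. This is an inexpensive improvement to a secondary analysis and no threat to the trial's main result.

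**What to change.** Replace the correlation sentence in the Statistical Analysis Plan with wording such as: *Correlations that use intraoperative, postoperative or change values will be estimated separately at each time point, with one value per patient, as partial Pearson or partial rank correlations controlling for flow group; the coefficient within each arm will be shown alongside.* Name the marker pairs and time points in the same place. Correlations among preoperative values can stay as plain Pearson or Spearman.

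The cost is one sentence and one degree of freedom (77 instead of 78 with 80 patients). No new data are needed. Under the assumptions above, adjustment keeps the error rate at about 5%. It also keeps power for a within-arm correlation of 0.30 at about 77% with 40 per group, whatever the size of the flow effect.

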In our study, two groups will be formed: low flow group and high flow group. Vitamin D, albumin, CRP, TAS, and TOS values will be checked from all patients before and during the operation. During the operation, 1 L/min fresh gas flow will be given to the low-flow group, 4 L/min fresh gas flow will be given to the high-flow group, and the processed EEG values of all patients will be monitored, and the same depth of anesthesia will be ensured. Albumin, CRP, TAS, and TOS values from the postoperative blood samples of the patients taken to the ward after the operation will be rechecked, and these values will be compared with the previous values.

Our study will compare the changes in total oxidant and total antioxidant systems in general anesthesia methods applied with 1 lt/min and 4 lt/min flows. Studies show patient-based advantages of low-flow anesthesia, such as respiratory functions and inflammatory response in the postoperative period. However, very few studies show its effects on oxidative stress, and a comprehensive study evaluating total oxidant/antioxidant systems was not found in our literature review. Therefore, our study will contribute to the literature.

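### The available SAP text names no primary variable, primary time or multiplicity rule, and does not say how TAS and TOS together answer the question about balance

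*Combined protocol and SAP*

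**What the plan says.** - **Question.** General Information/ Background asks "whether low-flow anesthesia positively contributes to the total oxidant/antioxidant balance". The Introduction puts the aim in terms of two systems: "Our study will compare the changes in total oxidant and total antioxidant systems in general anesthesia methods".
- **Sampling.** The Introduction says "Vitamin D, albumin, CRP, TAS, and TOS values will be checked from all patients before and during the operation", and then "Albumin, CRP, TAS, and TOS values from the postoperative blood samples of the patients taken to the ward after the operation will be rechecked". The procedures printed under Exclusion criteria put it differently: "Albumin, CRP, TAS, and TOS values will be rechecked in the postoperative blood samples of the patients during and after the operation". Neither place gives a clock time or interval for the postoperative sample.
- **Analysis.** The Statistical Analysis Plan chooses tests by type and distribution of data: t, Welch or Mann-Whitney for groups, chi-square or exact tests for categories, Pearson or Spearman for correlation. It adds that "A comparison of the values measured at different periods during the operation will be performed using repeated measures ANOVA". It closes with "the significance level will be taken as 0.05".
- **Success.** The only success criterion, in Success Criteria and Alternative Plan, is a weekly number of completed volunteers. It is not a criterion on outcome.

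The available text attaches no test to a named variable or time. It contains no primary outcome, multiplicity rule, ratio or index of TOS to TAS, or rule for reading the two markers together.

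**The concern.** Balance is a joint concept, and the plan supplies two separate measurements with nothing to link them. Two consequences follow.

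1. **No defined answer.** If TOS falls and TAS does not move, or both rise, the plan does not say whether balance improved. That reading would be chosen after the data are seen.
2. **More than one chance at 0.05.** TAS and TOS can each be tested at 0.05, possibly at more than one time. A difference in one of them could then be presented as the finding on balance, with a false-positive chance above that of a single test.

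**Working it through.** The available text gives no sample size, power, effect size or standard deviation, so there is no design figure to reproduce. The check is of the false-positive chance under the plan as written.

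**Inputs**
- Level per test: 0.05, unadjusted (Statistical Analysis Plan).
- Sidedness: not stated; two-sided assumed.
- Markers bearing on balance: 2, TAS and TOS (Introduction).
- Post-baseline occasions: 1 or 2. The Introduction lists samples during the operation and on the ward. The procedures under Exclusion criteria speak of postoperative samples taken during and after the operation, which can be read either way.
- Correlation between the test statistics: not given; 0, 0.7 and -0.7 assumed.

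**Chance of at least one false positive, either direction**

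For k independent tests: 1 - (1 - 0.05)^k.
- One test: 5%.
- TAS and TOS at one time, k = 2: 1 - 0.95^2 = 1 - 0.9025 = 0.0975, or 9.75%.
- TAS and TOS at two times, k = 4: 1 - 0.95^4 = 1 - 0.8145 = 0.1855 (0.18549 before rounding), or 18.5%.

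For two correlated tests: 1 - P(|Z1| < 1.96 and |Z2| < 1.96) under a bivariate normal distribution. At correlation 0.7 or -0.7 this is 0.0835 (0.08345 before rounding), or 8.3%.

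**Same calculation, favouring low flow only**

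A single two-sided test gives 2.5% in that direction. Two independent tests give 1 - 0.975^2 = 0.0494, or 4.9%.

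**Requiring both markers to improve**

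Assume 80% power for each marker at two-sided 0.05, so each test statistic has mean 1.96 + 0.84 = 2.80. The chance that both exceed 1.96 is:
- independent: 0.80 × 0.80 = 0.64;
- correlation -0.7: 0.60;
- correlation 0.7: 0.71.

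**Does a ratio as primary need a gate before TAS and TOS are tested?**

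Simulate no effect on either marker, with equal variances on the log scale (assumed). Test log(TOS/TAS) at 0.05, and test TAS and TOS under a Holm rule whatever the primary shows. The chance of any false positive is about 6% at correlation -0.7 and about 8.5% at 0.7. The latter is no better than the 8.3% for the two unadjusted tests. If TAS and TOS are tested only after a significant primary, it returns to 5%.

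**The case against.** - **Missing text may settle it.** One unavailable part lies between the study procedures and Success Criteria and Alternative Plan, where outcomes could be stated. A reader might infer that the trial has no primary outcome at all; the available text cannot show that. The Statistical Analysis Plan does read as continuous, however, and nothing in it refers back to a primary outcome. This objection stands as a condition and lowers confidence.
- **The focus is clear.** The Background and Introduction identify TAS and TOS as the markers of interest. That is right, and the gap is narrower than having no outcome of interest. What is open is their ranking or combination, and the time. Nor does any passage say that one marker would suffice. A reader might infer an intention to claim on a single marker, but the documents show only that the plan would permit it.
- **Repeated measures ANOVA may reduce the tests.** If it covers the blood markers, there could be one test per marker, which is the two-test case. But the sentence names no variable and no decisive effect (time, group or their interaction). It may concern the vital signs and BIS recorded every 5 minutes.
- **The inflation is modest in the direction of interest.** Two independent tests favouring low flow give 4.9%, below the nominal 5%. The excess is against the 2.5% that one two-sided test allows in that direction. This is fair, and it is why the result is not presented as a large excess of claims for low flow.
- **It is a small exploratory study.** The available text does not call it exploratory, and the Background states a directional expectation.

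**Conclusion.** The point holds for the available text, with medium confidence because of the parts that could not be checked. It should be corrected before results are seen.

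The firm part needs no assumption: the plan does not say which result on TAS and TOS, at which time, answers the question about balance. The size of the error depends on two-sided testing and on the number of tests. It is about 8% to 10% in either direction for two tests at one time, against 5% for one. The 18.5% figure applies only if the groups are compared at both an intraoperative and a postoperative sample and the four tests are independent. A reader might take it as the trial's false-positive rate; the documents do not support that, because the two descriptions of sampling leave the number of occasions unclear.

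**What to change.** Before results are seen, name one primary analysis at one stated postoperative sampling time. If an unavailable part already names a primary outcome, carry it into the Statistical Analysis Plan and state how discordant TAS and TOS are read. Otherwise, wording such as this would serve:

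> The primary outcome is log(TOS/TAS) in the postoperative sample taken at [stated time]. Groups are compared by a linear model with group and preoperative log(TOS/TAS) as terms, at two-sided 0.05. TAS and TOS are tested separately only if this result is significant, by Holm's method (smaller p-value against 0.025, then the other against 0.05). Otherwise they are reported as descriptive estimates with 95% confidence intervals. Albumin, CRP, other times, vital signs and correlations are exploratory.

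Three points go with it.
- The ratio appears nowhere in the available text. The investigators must confirm that it is what they mean by balance, since an equal proportional rise in both markers counts as no change.
- For the primary analysis, this model replaces the choice among t, Welch and Mann-Whitney tests.
- Requiring both TAS and TOS to improve is an alternative only if the investigators intend that stricter question, because balance could also improve through lower TOS with unchanged TAS. With an assumed 80% power per marker, joint power is about 60% to 71%.

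**Cost.** No new samples or assays: the preoperative values are already collected. The plan needs new wording and a stated postoperative sampling time. The price is that secondary and exploratory results no longer support claims at an unadjusted 0.05.

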### **Ethical Board Approval**

Duzce University Non-Invasive Health Research Ethics Committee; Date: 25.04.2022; Number: 2022/61

### **Funding**

Duzce University Scientific Projects Coordination Office; Project Number: 2022.04.02.1335
